6.1 Sample Size Determination

The sample size was determined for a two-sided two-sample t-test to test the difference in mean weight loss percentage between both treatment arms, assuming a mean weight loss of 6.75% (SD 7.12%) [unpublished, own retrospective data] in the control arm and a mean weight loss of 12% (SD 5.3) [unpublished, data provided by Pro Well] in the intervention arm. Assuming a 20% drop-out rate, a 5% significance level and 80% of power, a total sample size of 62 patients is indicated, or 31 patients per study arm

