6.2 Statistical Analysis

[The primary analysis will be performed using a two-sample two-sided t-test to test the difference in mean weight loss percentage between both treatment arms. Mean weight loss percentages and the mean difference in weight loss percentage will be estimated and presented with 95% confidence intervals. A 5% significance level will be adopted for the primary analysis. Given the pragmatic nature of the trial, the primary analysis will be performed following the intention-to-treat (ITT) principle, in that all randomized patients will be analyzed in the study arm in which they were randomized, regardless of adherence to the therapy assigned to the patient. In presence of missing outcome data due to drop-out of patients for whom

no follow-up data were collected, the method of multiple imputation will be used. Fully conditional specification will be used to create 10 complete data sets, of which each will be analyzed and analysis results combined according to multiple imputation principles. Treatment arm and previous weight loss measures will be used as predictors in the imputation model.

A per protocol (PP) analysis will be performed as a secondary analysis, including patients adherent to the randomized treatment. Missing data will be dealt with as described above, using multiple imputation.

Linear mixed models for longitudinal data will be used for the analysis of a treatment effect on weight loss percentage at other time points. The explanatory model will contain treatment arm, time point and the interaction thereof. A random effect for patient will be modelled to deal with data clustering. Results will be presented as mean differences per time point with 95% confidence intervals.

The treatment effect on the proportion of patients with weight loss at various time points will be analyzed using logistic regression analysis, with generalized estimating equations (GEE) to account for data clustering. The explanatory model will contain treatment arm, time point and the interaction thereof. Results will be presented as odds ratios per time point with 95% confidence intervals

The treatment effect on the time to reach a pre-defined weight loss percentage will be analyzed using a log-rank test for time-to-event outcomes. Additionally, a Cox model will be used for the estimation of the hazard ratio with 95% confidence interval.

Descriptive analyses will be used for tolerability or adherence to treatment.]

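### Ten imputations are valid but few for a 5% test: a primary result near p = 0.05 could fall on either side depending on the random seed

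*Protocol*

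**What the plan says.** Protocol section 6.2 makes the primary analysis a two-sided two-sample t-test at 5% on all randomised patients in their allocated arm. The sentence on missing outcomes begins "In presence of missing outcome data due to drop-out of patients for whom" and continues "no follow-up data were collected, the method of multiple imputation will be used". The number of imputations is given as a figure: "Fully conditional specification will be used to create 10 complete data sets". The predictors are also named: "Treatment arm and previous weight loss measures will be used as predictors in the imputation model". The table in section 6.2.1 repeats, without restriction, that multiple imputation is used for missing data in the primary analysis.

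Section 6.1 supplies the planning drop-out: "Assuming a 20% drop-out rate, a 5% significance level and 80% of power, a total sample size of 62 patients is indicated".

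In the Study Flowchart, weight is taken at randomisation and then at the in-clinic visits at weeks 10, 16, 26 and 52. Section 6 refers to a statistical analysis plan for detail. The number of data sets is nevertheless fixed in the protocol, so that plan could raise it only by departing from the protocol's text.

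**The concern.** Multiple imputation draws random values, so the pooled estimate, its standard error and the p-value all change with the seed. The change shrinks as the number of data sets grows. With about a fifth of outcomes missing and only ten data sets, it can be large enough to move a borderline result across 5%. Two analysts following section 6.2 correctly on the same database could then reach opposite conclusions on the primary hypothesis.

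A lesser point concerns the predictors. Weight is first re-measured at week 10, so for a patient who leaves before then treatment arm is the only listed predictor with a value. The imputed values are then random draws around the arm mean, which is where the seed matters most.

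**Working it through.** **Inputs from the Protocol.** Section 6.1: control mean 6.75 (SD 7.12), intervention mean 12 (SD 5.3), difference 12 − 6.75 = 5.25 points, 31 per arm, 20% drop-out, two-sided 5%, 80% power. Section 6.2: 10 data sets; predictors are arm and previous weight loss.

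**Assumed, because the Protocol does not give them.** Within-patient correlation 0.6 or 0.8; share of drop-outs who leave before week 10: 0, 50 or 100%.

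**Step 1: the plan's own sample size.** The root-mean-square SD is √[(7.12² + 5.3²)/2] = 6.28. By the noncentral t, 24 completers per arm give 80.8% power (Welch). Inflating, 24/0.80 = 30 per arm, or 60 in total; 25 completers give 25/0.80 = 31.25, rounded up to 32 per arm, or 64. The stated 62 lies between, so it reproduces. Twenty per cent of 31 is about 6 missing per arm.

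**Step 2: fraction of missing information (λ).** The section 6.2 imputation was simulated with 31 per arm and 6 missing per arm, pooled by Rubin's rules with small-sample degrees of freedom. λ was 0.08 to 0.12 if every drop-out had week-10 data, 0.14 to 0.17 if half did, and about 0.21 if none did. The range 0.10 to 0.20 is used below.

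**Step 3: efficiency.** Relative efficiency with m data sets is 1/(1 + λ/m). For m = 10 it is 1/(1 + 0.10/10) = 0.990 and 1/(1 + 0.20/10) = 0.980.

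**Step 4: spread of p across seeds, by formula.** The seed-to-seed SD of the estimate, in standard-error units, is √(λ/m). Take t = 2.0 with 48 degrees of freedom (p = 0.051) and t ± 1.96√(λ/m):

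| λ | m | √(λ/m) | t range | p range |
|---|---|---|---|---|
| 0.10 | 10 | 0.100 | 1.80 to 2.20 | 0.033 to 0.078 |
| 0.10 | 50 | 0.045 | 1.91 to 2.09 | 0.042 to 0.062 |
| 0.10 | 100 | 0.032 | 1.94 to 2.06 | 0.045 to 0.059 |
| 0.20 | 10 | 0.141 | 1.72 to 2.28 | 0.027 to 0.091 |
| 0.20 | 50 | 0.063 | 1.88 to 2.12 | 0.039 to 0.067 |
| 0.20 | 100 | 0.045 | 1.91 to 2.09 | 0.042 to 0.062 |

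**Step 5: the same by simulation.** The formula leaves out the seed noise in the standard error, so simulated ranges are somewhat wider. Data were shifted so that the many-imputation p was about 0.05. Central 95% of p across seeds:

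| Correlation | Drop-outs before week 10 | m = 10 | m = 50 | m = 100 |
|---|---|---|---|---|
| 0.6 | none | 0.030 to 0.091 | 0.040 to 0.065 | 0.044 to 0.060 |
| 0.6 | all | 0.023 to 0.112 | 0.036 to 0.071 | 0.040 to 0.064 |
| 0.8 | none | 0.031 to 0.076 | 0.040 to 0.058 | 0.042 to 0.055 |
| 0.8 | all | 0.026 to 0.114 | 0.037 to 0.074 | 0.041 to 0.067 |

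With m = 10 the seed SD of the estimated difference was 0.15 to 0.20 points with no early drop-out and 0.26 to 0.27 with all early, against a standard error of 1.6 to 1.9.

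**Step 6: how often it matters.** In 8,000 simulated trials per setting, with all drop-outs early (the least favourable case), two seeds disagreed on p < 0.05 as follows. At the planned difference of 5.25: 5.8% (m = 10), 2.2% (50), 1.5% (100). At a difference of 3.6: 8.4%, 3.3%, 2.7%.

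**The case against.** The strongest reply is that ten imputations are not an error. Rubin's rules carry a (1 + 1/m) term for the finite number of data sets. An approximation at λ = 0.16 gives type I error of about 4.5% with 10 or 50, and power of 83.5% against 84.2%. This stands: the concern is reproducibility of a borderline decision, not bias or validity.

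Second, more imputations do not abolish the problem. The ranges for 50 and 100 still straddle 0.05. That also stands, and the benefit should be described as a reduction. A seed is an ordinary detail of a statistical analysis plan, so its absence from the Protocol is not a fault.

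Two stronger readings are tempting, and the document does not support them.

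- A reader might infer that imputation is confined to patients with no post-baseline data, leaving others without a week-26 weight outside the analysis. Section 6.2 analyses all randomised patients and uses earlier weight loss as a predictor, which makes sense only if patients with some follow-up are imputed too. Section 6.2.1 sets no restriction. The wording is loose, but every patient lacking a week-26 weight is covered.
- A reader might infer that leaving out baseline weight, regain, surgery type, site and week-52 weight wastes material information. The Protocol gives no correlation between these and the outcome. With an assumed multiple correlation of 0.1, 0.3 or 0.5 and 8% lost before week 10, the recoverable information is roughly 0.1%, 0.7% or 2%. The endpoint is already scaled by baseline weight, and five extra predictors with about 50 observed outcomes is a trade-off.

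**Conclusion.** The point holds as a minor, near-costless improvement. Section 6.2 fixes ten data sets, which is valid and about 98% efficient at λ = 0.20. If the many-imputation p is near 0.05, the reported p could fall anywhere from roughly 0.03 to 0.08 (λ = 0.10) or 0.025 to 0.11 (λ = 0.20), against about 0.04 to 0.06 or 0.04 to 0.07 with 50 to 100. Results well away from 0.05 are unaffected.

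The size rests on the 20% planning drop-out, which is not an observed missing rate, and on the assumed correlations and timing of drop-out. Most of the seed dependence comes from the number of data sets: it is present even when no patient leaves early. The short predictor list only widens it.

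**What to change.** In section 6.2, replace ten data sets with at least 100 (50 as a minimum), and state that the seed is set before the data are analysed. The seed prevents choosing among runs; the larger number reduces the noise. The cost is one sentence and minutes of computing, with no new data.

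Optional: consider a short addition to the imputation model, such as baseline weight and the week-52 weight where available. Keep the list short with 62 patients, and do not expect a large gain.

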6.2.1 Efficacy Analysis

Endpoint	Statistical Analysis Methods
Primary	Two-sided two sample t-test, with analysis following the intention-to-treat principle and multiple imputation to deal with missing data.
Secondary (if applicable)	Linear mixed models for continuous and longitudinal data. Logistic regression for binary and longitudinal data. Log-rank test and Cox model for time-to-event data. Descriptive statistics for adherence and tolerability.

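### Ten imputations are valid for the primary analysis but leave avoidable seed noise that can tip a borderline p-value; 100 would remove most of it at almost no cost

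*Protocol*

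**What the plan says.** Section 6.2 makes a single test confirmatory: "The primary analysis will be performed using a two-sample two-sided t-test to test the difference in mean weight loss percentage between both treatment arms". It adds: "A 5% significance level will be adopted for the primary analysis". The analysis follows intention to treat. Missing outcomes are handled as follows: "Fully conditional specification will be used to create 10 complete data sets", each analysed separately and then combined. The imputation model is limited: "Treatment arm and previous weight loss measures will be used as predictors in the imputation model". The per-protocol analysis refers back to the same procedure. Section 6.2.1 repeats that the primary analysis uses "multiple imputation to deal with missing data".

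Section 6.1 shows how much missing data is expected: "Assuming a 20% drop-out rate, a 5% significance level and 80% of power", with 31 patients per arm.

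The opening of section 6 leaves the detailed description to an SAP that is not shown. The number of imputations, however, is set in the protocol itself.

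**The concern.** Multiple imputation draws random values, so the pooled difference and its p-value depend on the random number stream unless the number of imputations is large. Here about a fifth of the primary outcomes may be imputed, the trial is small, and superiority is judged by one p-value against a fixed 5% threshold. If the data give a p-value close to 5%, an arbitrary seed could help decide on which side it falls. Efficiency, the usual argument for a small number of imputations, does not address that.

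**Working it through.** **Inputs from the protocol.** Section 6.1: 31 per arm; week-26 weight loss 6.75% (SD 7.12) in control and 12% (SD 5.3) in intervention, a difference of 5.25 points; 20% drop-out; two-sided 5%; 80% power. Section 6.2: m = 10 imputations, with arm and earlier weight loss as predictors.

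**Assumptions not in the protocol.** Correlations between weight-loss measures of 0.5-0.9; interim means at 60% and 80% of the week-26 mean; drop-out completely at random, 6 of 31 per arm; drop-outs either have no interim weights or leave evenly before weeks 10, 16 and 26.

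**Step 1: the plan's own figure.** Root-mean-square SD = √((7.12² + 5.3²)/2) = 6.276. The noncentral t calculation needs 24 per arm (power about 81%), and 24/0.8 = 30 per arm, or 60 in total. That is within two patients of the stated 62. With 31 × 0.8 = 24.8 per arm remaining, power is about 82%, and the standard error is about 6.276 × √(2/24.8) = 1.78 points.

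**Step 2: Monte Carlo error by formula.** The seed-to-seed SD of the pooled difference is √(B/m), where B is the between-imputation variance. As a fraction of the standard error this is √(FMI/(m+1)), where FMI is the fraction of missing information. Relative efficiency is 1/(1 + FMI/m).

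| FMI | m = 10 | m = 50 | m = 100 | Efficiency at m = 10 |
|---|---|---|---|---|
| 0.10 | 0.095 | 0.044 | 0.031 | 0.990 |
| 0.20 | 0.135 | 0.063 | 0.044 | 0.980 |

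**Step 3: the same in points, by simulation.** Imputation was sequential Bayesian regression on arm and earlier weight loss, followed by a t-test per data set and Rubin's rules with small-sample degrees of freedom.

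| Correlation, drop-out pattern | FMI | √B | SD, m = 10 | SD, m = 50 | SD, m = 100 |
|---|---|---|---|---|---|
| 0.5, no interim weights | 0.208 | 0.830 | 0.262 | 0.117 | 0.083 |
| 0.7, spread over time | 0.153 | 0.670 | 0.212 | 0.095 | 0.067 |
| 0.9, spread over time | 0.103 | 0.540 | 0.171 | 0.076 | 0.054 |

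In a more favourable setting, with nobody lost before week 10 and correlations of 0.72-0.85, the SD at m = 10 is about 0.135. About 0.15-0.25 points is therefore a fair summary.

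**Step 4: effect on the p-value for a fixed data set.** Three data sets per setting were each re-imputed 300 times, so these ranges are approximate.

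| p with many imputations | Seeds on the other side of 0.05, m = 10 | m = 100 |
|---|---|---|
| about 0.01 | 0-0.8% | 0% |
| about 0.03 | 2-16% | at most 0.1% |
| about 0.04 | 20-36% | 2-13% |
| about 0.06 | 24-31% | 2-11% |

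**Step 5: effect over whole trials.** Share of trials in which two independent runs disagree on p<0.05 (correlation 0.7, 300 trials per row):

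| True difference, pattern | m = 10 | m = 50 | m = 100 |
|---|---|---|---|
| 5.25, no interim weights | 4.3% | 2.0% | 2.7% |
| 5.25, spread over time | 4.0% | 1.0% | 1.0% |
| 3.5, no interim weights | 8.0% | 3.3% | 2.0% |
| 3.5, spread over time | 6.3% | 3.7% | 2.3% |

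The simulation error of a 4% entry is √(0.04 × 0.96/300) = 1.1 percentage points, so 50 and 100 imputations are not separated here. With correlations of 0.72-0.85 and none, half or all of the drop-out before week 10, disagreement at m = 10 and 5.25 points is about 2%, 4% and 6%. With no early loss and a difference of 3.8 points it is about 3%.

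**The case against.** The strongest defence is that nothing here is invalid. Rubin's rules already charge a finite number of imputations to the standard error and degrees of freedom, the estimate is unbiased, and efficiency is about 98%. Seed noise of 0.15-0.25 points is small beside a standard error of 1.8. All of this stands, and it limits the point to an improvement. It does not answer the question of stability against a fixed threshold.

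A second defence is that the SAP may fix a seed, which would make a re-run on the same software repeatable. That also stands. A reader might infer that a second statistician following this plan could reach the opposite conclusion. The protocol does not support that, because it leaves the detailed analysis to an SAP that is not shown. What remains is dependence on an arbitrary, though pre-set, seed. For the same reason, the protocol's silence on the seed and on the pooling degrees of freedom is not a fault.

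A third defence is that the high flip rates in step 4 are conditional on a borderline result. This is correct. Under the planning assumptions, p lies between 0.03 and 0.045 in only about 5% of trials. If 14-31% of seeds cross 0.05 in that band, it contributes 0.05 × 0.14 = 0.7% to 0.05 × 0.31 = 1.6% of trials.

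**Conclusion.** The point holds as a modest, inexpensive improvement to a value that the protocol itself fixes. At m = 10 two arbitrary seeds disagree on significance in about 2-6% of trials at the planned difference and about 3-8% at 3.5-3.8 points. With 100 imputations this is about 0-3%, so it is reduced but not abolished. Almost all affected trials have p of roughly 0.02-0.10; a result near 0.01 is practically safe.

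It would go too far to say that the random number stream decides whether superiority is declared. That can happen only near the threshold, and the unconditional figures are small.

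The sizes rest on the assumed correlations, drop-out timing and missingness completely at random. The differences of 3.5 and 3.8 points are illustrations of a smaller effect, not protocol figures. The wording "In presence of missing outcome data due to drop-out of patients for whom" no follow-up data exist leaves the timing open. If it means no post-baseline weights at all, FMI is about 0.20-0.21, the upper end. If some interim weights exist, it is about 0.10-0.18.

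**What to change.** In section 6.2, change the number of imputed data sets from 10 to 100 (at least 50), and state that the same number applies to the per-protocol analysis. Make the change before week-26 outcomes are analysed. The cost is one number in the text and seconds of computing, with no burden on patients or sites. The random seed and the degrees of freedom for pooling can be left to the SAP.

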Study rationale	Bariatric surgery induces substantial weight loss and reduction in obesity-related comorbidities. Despite the major benefits of bariatric, some patients still regain weight post-operatively. This is the reason why we want to investigate the influence of a pharmacotherapeutic treatment (naltrexone/bupropion) on weight regain after bariatric surgery. This multicenter, randomized clinical trial will compare the outcomes of two different groups: all participants will receive intensive lifestyle management and naltrexone/bupropion, and one experimental group will in addition follow a very low calorie ketogenic diet (VLCKD).
Primary objective	To evaluate the superiority of combined VLCKD, intensive lifestyle intervention and naltrexone/bupropion versus standard of care with naltrexone/bupropion on weight loss.
Secondary objective(s)	To describe changes in metabolic health parameters and health-related quality of life during combined treatment of VLCKD, intensive lifestyle program and naltrexone/bupropion versus standard of care alone with naltrexone/bupropion.
Study design	Prospective Multicentric Longitudinal Randomized Controlled Study
Endpoints	Primary endpoints • The percentage of weight loss at 26 weeks Secondary endpoints • A weight loss percentage at 10 weeks, 16 weeks and at end of trial (= 52 weeks from start)

	
• A proportion of patients with a weight loss percentage of 5% or more at 10, 16, 26 and 52 weeks• A proportion of patients with a weight loss percentage of 10% or more at 10, 16, 26 and 52 weeks• The time to reach a weight loss percentage of 5% and 10%• The dose of naltrexone/bupropion used at 10, 16, 26 and 52 weeks and at the end of the trial• The tolerability of VLCKD and NB• The adherence to VLCKD and NB• The Patient-Reported Outcome Measures (PROMs) of hunger and cravings at 0, 4, 10, 16, 26 and 52 weeks• The change in fasting glucose, lipids and blood pressure at 10, 16, 26 and 52 weeks
Sample Size	
• Experimental/treatment arm: 31 patients• Comparator arm: 31 patients• Total: 62 patients
Third parties	
• Pro Well
◦ Provide VLCKD◦ Provide Lifestyle program• Goodlife Pharma
◦ Provide Mysimba tablets

STUDY FLOWCHART

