Procedures/assessments	Phase 0: Screening and randomization		Phase 1: Lifestyle + NB with vs without VLCKD							Phase 2: Lifestyle + NB (all participants)				Follow-up (all participants)		
	Screening (In-clinic)	Randomization (in-clinic)	Remote	Remote	Remote	Remote	Remote	Remote	In-clinic (study specific)	Remote	Remote	In-clinic (Routine)	Remote	Remote	In-clinic (study specific)	In-clinic (routine)
Visit	V1	V2	V3	V4	V5	V6	V7	V8	V9	V10	V11	V12	V13	V14	V15	V16
Timing of visits (weeks)		Start	Start	W3	W4	W6	W8	W10	W10	W12	W16	W16	W20	W26	W26	W52
Visit window (days)									±30			±30			±30	±30
Lifestyle program			X		X		X			X	X		X	X		
Naltrexone/bupropion (NB)		X							X			X			X	X
VLCKD			(X) ¹	(X) ¹	(X) ¹	(X) ¹	(X) ¹	(X) ¹								
Screening assessments and randomization																
Informed consent	X ²															
Inclusion/exclusion criteria	X	X														
Randomization		X														
Anthropometric data (height, weight, waist circumference)		X							X			X			X	X

Clinical examination (Blood pressure, heart and lung auscultation, abdominal palpitation and percussion)		X							X			X				X	X
Laboratory tests																	
Fasting glucose		X							X			X				X	X
Hemoglobin A1c		X										X					X
Lipids: LDL-cholesterol, HDL-cholesterol, triglycerides		X							X			X				X	X
Liver test: AST, ALT, gamma-GT, alkaline phosphatase, total bilirubin, albumin		X										X					X
Kidney function: creatinine, eGFR		X										X					X
Thyroid function: TSH, free T4		X										X					X
Uric acid		X										X					X
Questionnaires																	
The PsyEndoAUDIT questionnaire ³		X							X			X				X	X
The PsyEndoCIDI questionnaire ³		X							X			X				X	X
The PsyEndoEDE questionnaire ³		X							X			X				X	X
The PsyEndoHADS questionnaire ³		X							X			X				X	X
Nederlandse vragenlijst voor eetgedrag ³		X							X			X				X	X
The ObesitasIPAQ questionnaire ³		X							X			X				X	X

The quality of life (SF-36) questionnaire ³		X							X				X			X	X
The outtake questionnaire															X		
Reason for discontinuation		X							X			X			X	X	
(Serious) Adverse event (S)(AE) assessment		X							X			X			X	X	

- Depending on randomization in either intervention (with VLCKD) or comparator group (without VLCKD).
- Informed Consent must be obtained prior to performing any other Trial-related procedures as part of the standard of care.
- See appendix 4 for the respective questionnaires.

I Background and Rationale

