2.3 Secondary Endpoints

- A weight loss percentage at 10 weeks, 16 weeks and at end of trial (= 52 weeks from start)
- A proportion of patients with a weight loss percentage of 5% or more at 10, 16, 26 and 52 weeks
- A proportion of patients with a weight loss percentage of 10% or more at 10, 16, 26 and 52 weeks
- The time to reach a weight loss percentage of 5% and 10%
- The dose of naltrexone/bupropion used at 10, 16, 26 and 52 weeks and at the end of the trial
- The tolerability of VLCKD and NB
- Adherence to VLCKD and NB
- The Patient-Reported Outcome Measures (PROMs) of hunger and cravings at 0, 4, 10, 16, 26 and 52 weeks
- The change in fasting glucose, lipids and blood pressure at 10, 16, 26 and 52 weeks]

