5.1.5 Pharmacovigilance

Any adverse reactions related to the medicinal products used by the participants in the study, can be reported to the Marketing Authorisation Holder and/or the Competent Authorities according to the pharmacovigilance guidelines.

6 Statistics and Data Analysis

Statistical analysis will be performed in accordance with ICH E9; a detailed description of the analysis is provided in the Trial-specific Statistical Analysis Plan (SAP). ICH E3 and E8 will guide the structure and content of the clinical trial report.

[The hypothesis for this trial is that the percentage of weight loss will be greater for the experimental arm than the comparator arm.]

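### The only mixed model the protocol specifies has no baseline term, so change in fasting glucose, lipids and blood pressure would be compared without using the V2 value for adjustment (minor, secondary endpoints)

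*Protocol*

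**What the plan says.** Section 2.3 of the protocol lists as a secondary endpoint "The change in fasting glucose, lipids and blood pressure at 10, 16, 26 and 52 weeks". The Study Flowchart schedules fasting glucose, lipids and the clinical examination, which includes blood pressure, at V2 (randomisation) and at each of these four time points. A baseline value is therefore planned for every patient.

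Section 6.2 introduces its mixed model for a different endpoint: "Linear mixed models for longitudinal data will be used for the analysis of a treatment effect on weight loss percentage at other time points". It then gives the fixed part, "The explanatory model will contain treatment arm, time point and the interaction thereof", and the random part, "A random effect for patient will be modelled to deal with data clustering". The sentence on fixed effects recurs in the next paragraph for the GEE logistic model, again for weight loss. Section 6.2 has no paragraph on glucose, lipids or blood pressure.

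These endpoints are reached only through the table in 6.2.1, which assigns to the secondary endpoints "Linear mixed models for continuous and longitudinal data" and names no covariates. Baseline adjustment is not mentioned anywhere in Section 6. The opening of Section 6 refers to a statistical analysis plan for detail; that plan is not among the documents at hand.

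**The concern.** The metabolic endpoints are defined as change from a value measured at V2. A change score subtracts the whole baseline value, although the follow-up value is usually only partly predicted by it. A patient who happens to start high tends to fall in either arm, so a chance difference between arms at V2 enters the estimated effect with the opposite sign. Including the V2 value in the model removes this component of error.

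What is at stake is precision on the metabolic part of the secondary objective. The trial randomises 31 patients per arm, or about 25 per arm after the 20% drop-out that Section 6.1 assumes (0.8 x 31 = 24.8). At that size, free precision is worth taking.

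**Working it through.** **Plan's own figure.** The protocol gives no SD, correlation or target precision for glucose, lipids or blood pressure. Its only calculation is the total of 62 for weight loss percentage (6.1). The inputs are a difference of 12 - 6.75 = 5.25, SDs of 7.12 and 5.3 (root mean square 6.276), two-sided 5% and 80% power. The t-test needs 24 per arm, and 24/0.8 = 30 per arm, or 60 in total. This agrees with 62 to within two patients and does not bear on the present point.

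**Inputs.** n = 31 per arm (6.1) and 1:1 allocation (4.3). Assumed: equal SD at baseline and follow-up, and a correlation rho between them, shown as a range.

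**Formulas.** Variance of the arm difference at one visit, in units of SD squared:
- unadjusted change: (2/n) x 2(1 - rho)
- adjusted for the V2 value: (2/n) x (1 - rho^2)
- ratio: (1 - rho^2) / [2(1 - rho)] = (1 + rho)/2, so the variance saved is (1 - rho)/2
- reduction in interval width: 1 - sqrt[(1 + rho)/2]

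| Assumed rho | Variance saved | Width saved |
|---|---|---|
| 0.4 | 30% | 16% |
| 0.5 | 25% | 13% |
| 0.6 | 20% | 11% |
| 0.7 | 15% | 8% |
| 0.8 | 10% | 5% |
| 0.9 | 5% | 2.5% |

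Example: at rho = 0.5 and n = 31, the SE is sqrt(2/31 x 1) = 0.254 SD unadjusted and sqrt(2/31 x 0.75) = 0.220 SD adjusted.

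**Simulation** (20,000 trials per setting, no true effect). The adjusted-to-unadjusted variance ratios for rho 0.4, 0.5 and 0.7 were 0.72, 0.76 and 0.86 at 31 per arm, and 0.71, 0.77 and 0.87 at 25 per arm. The formula gives 0.70, 0.75 and 0.85; the slightly smaller gain in most settings is the price of estimating the baseline slope.

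**Bias and type I error.** In the same simulations the unadjusted comparison had a mean error of at most 0.006 SD and a type I error of 4.8% to 5.2%.

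**Effect of chance imbalance.** The baseline difference between arms has SD sqrt(2/31) = 0.254 baseline SD, and it exceeds 0.25 SD in either direction in about 32% of trials. The unadjusted estimate moves by -(1 - rho) times that difference; simulated slopes at 31 per arm were -0.595, -0.505 and -0.303 for rho 0.4, 0.5 and 0.7. For an imbalance of one standard deviation (0.254) at rho = 0.5, the shift is 0.5 x 0.254 = 0.127 SD, half of the unadjusted SE of 0.254.

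**Could the listed terms adjust by another route?** Suppose V2 enters as the first outcome time point, with arm, time and their interaction all free. With complete data, the interaction contrast against V2 is exactly the unadjusted change difference. The mean differences per time point, which 6.2 says will be reported, are then raw follow-up differences. These are unadjusted too: the adjusted variance is 1 - rho^2 of theirs, or 84%, 75% and 51% for rho 0.4, 0.5 and 0.7. The gain returns only if the baseline means are constrained equal across arms, which the protocol does not say.

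**The case against.** **The sentence is about weight loss percentage.** This is correct. Its use for glucose, lipids and blood pressure is an inference from the generic line in 6.2.1. A reader might infer that the protocol rules out baseline adjustment for these endpoints; it does not say so. It is nevertheless the only continuous model that the protocol describes, so it is the natural one to carry over.

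**Covariates for secondary endpoints belong in the SAP.** This largely stands, and the SAP may already settle the matter. What keeps the point alive is that 6.2 is not silent: it lists the terms of its model, and under either way of entering V2 those terms give an unadjusted contrast.

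**The objective is descriptive.** The synopsis does word it as "To describe changes in metabolic health parameters and health-related quality of life". It goes on to compare the combined treatment with standard of care, and 6.2.1 keeps descriptive statistics for adherence and tolerability. A between-arm estimate is therefore intended. The wording does limit how much weight the point can bear.

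**Regression to the mean cannot mislead a randomised comparison.** A reader might infer that unadjusted change would systematically create or conceal an effect. Allocation is randomised, and the simulations show no bias and nominal type I error. The shift with chance imbalance is part of the sampling error that the unadjusted interval already covers. Only the loss of precision, and the error conditional on the observed imbalance, remain.

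**Conclusion.** The point holds as a minor matter of efficiency. Applied to the metabolic change endpoints, the terms listed in 6.2 leave the V2 value unused for adjustment. The gain from using it is (1 - rho)/2 of the variance: 30% to 15% for an assumed rho of 0.4 to 0.7, and 10% to 5% for 0.8 to 0.9. These are variance figures. A reader might take 15% to 30% as the narrowing of the confidence intervals, but that is only about 8% to 16%.

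The figures rest on equal SDs at baseline and follow-up and on a correlation that the protocol does not give. The conclusion also assumes that the model in 6.2 is the one meant by 6.2.1. Validity is not in question, and neither the primary analysis nor the sample size is affected.

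**What to change.** Add to 6.2, and carry into the SAP: for fasting glucose, LDL-cholesterol, HDL-cholesterol, triglycerides, and systolic and diastolic blood pressure, the linear mixed model contains arm, visit, arm x visit, the V2 value of that measure, and V2 value x visit. Modelling V2 as an outcome time point with baseline means constrained equal across arms is an equivalent choice; the text should name one of the two.

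The cost is the added wording and a few degrees of freedom: with four follow-up visits, four extra coefficients per endpoint (one for the V2 value and three for its interaction with visit). The data are already scheduled at V2. Stating the choice before the data are analysed also closes off a later selection among raw, change and adjusted estimates.
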